- The percentages of patients with an AST measurement $\geq 3 \times$, $5 \times$, and $10 \times$ the central laboratory ULN during the treatment period will be summarized for all patients with a postbaseline value and for subsets based on various levels of baseline. Analyses will be constructed as described above for ALT.
- The percentages of patients with a total bilirubin measurement $\geq 2 \times$ the central laboratory ULN during the treatment period will be summarized for all patients with a postbaseline value and subset into 4 subsets: patients whose nonmissing maximum baseline value is $\leq 1 \times \text{ULN}$, patients whose maximum baseline is $>1 \times \text{ULN}$ but $<2 \times \text{ULN}$, patients whose maximum baseline value is $\geq 2 \times \text{ULN}$, and patients whose baseline values are missing.
- The percentages of patients with an ALP measurement $\geq 1.5 \times$ the central laboratory ULN during the treatment period will be summarized for all patients with a postbaseline value and subset into 4 subsets: patients whose nonmissing maximum baseline value is $\leq 1 \times \text{ULN}$, patients whose maximum baseline is $>1 \times \text{ULN}$ but $<1.5 \times \text{ULN}$, patients whose maximum baseline value is $\geq 1.5 \times \text{ULN}$, and patients whose baseline values are missing.

A by-patient listing will be provided for an ALT or AST measurement $\geq 3 \times \text{ULN}$, or with an ALP measurement $\geq 1.5 \times \text{ULN}$, or with a total bilirubin measurement $\geq 2 \times \text{ULN}$. The listing will include relevant demographic, study drug, concomitant therapy, AEs, and laboratory data.

To further evaluate potential hepatotoxicity, an Evaluation of Drug-Induced Serious Hepatotoxicity (eDISH) plot will be created. Each patient with at least 1 post-baseline ALT and total bilirubin contributes 1 point to the plot. The points correspond to maximum total bilirubin and maximum ALT, even if not obtained from the same blood draw.

Criteria for AE grading from the Common Terminology Criteria for Adverse Events (CTCAE) will be applied for the hepatic laboratory tests AST, ALT, ALP, total bilirubin, and albumin ([Table 6-3](#)). These CTCAE grading schemes are consistent with both Version 3.0 and Version

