4.03 of the CTCAE guidelines. When deriving CTCAE grades for laboratory analytes with absolute criteria for grading, such as albumin, an adjustment to the CTCAE-defined approach will be made. The use of a lower limit of normal/upper limit of normal (LLN/ULN) from appropriate reference ranges will be replaced with a simpler approach that uses a single value. This adjustment to the CTCAE grading criteria overcomes the irresolute derivation of the grade that can occur when some demographically-specific LLN/ULN values (from either the Lilly LCTPB or the Quintiles reference ranges) overlap with the CTCAE-defined value that separates normal (Grade 0) and Grade 1.

Table 6-3. Common Terminology Criteria for Adverse Events Related to Hepatic Tests

Laboratory Test	Laboratory Units	Grade	Criteria
Albumin	SI	0 (normal)	$\geq 35 \text{ g/L}$
		1	$<35 \text{ g/L}$ and $\geq 30 \text{ g/L}$
		2	$<30 \text{ g/L}$ and $\geq 20 \text{ g/L}$
		3	$<20 \text{ g/L}$
ALT	SI	0 (normal)	$\leq \text{ULN}$
		1	$>\text{ULN}$ and $\leq 2.5 \times \text{ULN}$
		2	$>2.5 \times \text{ULN}$ and $\leq 5 \times \text{ULN}$
		3	$>5 \times \text{ULN}$ and $\leq 20 \times \text{ULN}$
		4	$>20 \times \text{ULN}$
AST	SI	0 (normal)	$\leq \text{ULN}$
		1	$>\text{ULN}$ and $\leq 2.5 \times \text{ULN}$
		2	$>2.5 \times \text{ULN}$ and $\leq 5 \times \text{ULN}$
		3	$>5 \times \text{ULN}$ and $\leq 20 \times \text{ULN}$
		4	$>20 \times \text{ULN}$
ALP	SI	0 (normal)	$\leq \text{ULN}$
		1	$>\text{ULN}$ and $\leq 5 \times \text{ULN}$
		2	$>5 \times \text{ULN}$ and $\leq 20 \times \text{ULN}$
		3	$>20 \times \text{ULN}$
		4	$>20 \times \text{ULN}$
Total bilirubin	SI	0 (normal)	$\leq \text{ULN}$
		1	$>\text{ULN}$ and $\leq 1.5 \times \text{ULN}$
		2	$>1.5 \times \text{ULN}$ and $\leq 3 \times \text{ULN}$
		3	$>3 \times \text{ULN}$ and $\leq 10 \times \text{ULN}$
		4	$>10 \times \text{ULN}$

Abbreviations: ALP = alkaline phosphatase; ALT = alanine transaminase; AST = aspartate aminotransferase; ULN = upper limit of normal.

Treatment-emergent laboratory abnormalities related to hepatic abnormalities occurring at any time during the treatment period will be tabulated. Treatment-emergence will be characterized using 2 criteria (as appropriate to the grading scheme):

- any increase in post-baseline CTCAE grade from worst baseline grade
- an increase from worst baseline less than Grade 3 to Grade 3 or Grade 4 at worst post-baseline

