Treatment comparisons will be made using the Fisher exact test as appropriate. Scheduled and unscheduled measurements will be included.

Treatment-emergent laboratory abnormalities related to hepatic abnormalities shift tables of baseline to maximum during the treatment period will be tabulated. Shift tables will show the number and percent of patients with measurement in each category based on baseline to maximum CTCAE grade during the treatment period (Part A and B), with baseline depicted by the most extreme grade during the baseline period. A shift table summary displaying the number and percent of patients with maximum postbaseline results will be presented overall and by treatment group within the following categories:

- Decreased; post-baseline category < baseline category,
- Increased; post-baseline category > baseline category,
- Same; post-baseline category = baseline category.

The number and percent of patients with treatment-emergent hepatic laboratory abnormalities based on CTCAE grades will be summarized in terms of shift tables descriptively comparing baseline to maximum and last post-treatment follow-up grade and follow-up baseline to maximum and last post-treatment follow-up grade by treatment group. A shift table summary for each analysis will also be included. Furthermore, a summary of grade increases by each maximum and last grade will be provided.

First shift table summary:

- Decreased; maximum post-treatment follow-up category < baseline category
- Increased; maximum post-treatment follow-up category > baseline category
- Same; maximum post-treatment follow-up category = baseline category

Second shift table summary:

- Decreased; maximum post-treatment follow-up category < follow-up baseline category
- Increased; maximum post-treatment follow-up category > follow-up baseline category
- Same; maximum post-treatment follow-up category = follow-up baseline category

Third shift table summary:

- Decreased; last post-treatment follow-up category < baseline category
- Increased; last post-treatment follow-up category > baseline category
- Same; last post-treatment follow-up category = baseline category

Fourth shift table summary:

- Decreased; last post-treatment follow-up category < follow-up baseline category
- Increased; last post-treatment follow-up category > follow-up baseline category
- Same; last post-treatment follow-up category = follow-up baseline category

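### SAP Table 6-3 gives ALP Grades 3 and 4 the same criterion and puts >5 to 20 x ULN in Grade 2, so the graded ALP tables lose sensitivity

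*SAP*

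**What the plan says.** SAP Section 6.14.4.1 states that CTCAE grading "will be applied for the hepatic laboratory tests AST, ALT, ALP, total bilirubin, and albumin", and says that its schemes agree with CTCAE 3.0 and 4.03. Table 6-3 holds the criteria. For ALP they are:

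- Grade 0: up to ULN
- Grade 1: above ULN, up to 5 x ULN
- Grade 2: above 5, up to 20 x ULN
- Grade 3: above 20 x ULN
- Grade 4: above 20 x ULN

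Two treatment-emergence criteria run on these grades. The first is "any increase in post-baseline CTCAE grade from worst baseline grade". The second is "an increase from worst baseline less than Grade 3 to Grade 3 or Grade 4 at worst post-baseline". The arms are compared by Fisher's exact test as appropriate.

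The same grades feed the shift displays: "Shift tables will show the number and percent of patients with measurement in each category based on baseline to maximum CTCAE grade". A summary then classes each patient as decreased, increased or same. Four follow-up shift summaries and a summary of grade increases use the same rows.

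Outside the grades, the section plans one patient count for ALP, at >=1.5 x ULN, split by baseline level, and a by-patient listing at the same threshold. ALT and AST have counts at 3, 5 and 10 x ULN.

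**The concern.** A scale with two identical top grades cannot be applied as printed, because a value above 20 x ULN meets both definitions. The rest of the ALP ladder also looks displaced. Its Grade 2 range is the Grade 3 range of ALT and AST, and the step at 2.5 x ULN is absent.

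If the laboratory program follows the table literally, the grade-based ALP displays react later than a reader used to the ALT and AST rows would expect. ALP has only one other threshold count, at 1.5 x ULN. The grade tables are therefore the only planned patient counts that separate the higher ALP levels.

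**Working it through.** The plan gives no calculated figure to reproduce here. The check applies the printed rows literally and compares them with the other rows of Table 6-3.

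**Inputs (SAP Table 6-3, multiples of ULN)**

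| Grade | ALT and AST | ALP | Total bilirubin |
|---|---|---|---|
| 1 | >1 to 2.5 | >1 to 5 | >1 to 1.5 |
| 2 | >2.5 to 5 | >5 to 20 | >1.5 to 3 |
| 3 | >5 to 20 | >20 | >3 to 10 |
| 4 | >20 | >20 | >10 |

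Albumin is graded 0 to 3 and has no Grade 4 row. So where this table has no fourth grade, it leaves the row out. ALT, AST and bilirubin each have four distinct grades. ALP alone repeats a criterion.

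**Step 1. Grade each value from a Grade 0 baseline.** The last three columns show whether the planned displays pick it up. The ALT/AST column is for comparison only.

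| ALP (x ULN) | Grade as printed | Grade on ALT/AST rows | Any increase (as printed) | Grade 3 or 4 (as printed) | >=1.5 x ULN count |
|---|---|---|---|---|---|
| 1.2 | 1 | 1 | yes | no | no |
| 2.6 | 1 | 2 | yes | no | yes |
| 5 | 1 | 2 | yes | no | yes |
| 5.1 | 2 | 3 | yes | no | yes |
| 10 | 2 | 3 | yes | no | yes |
| 20 | 2 | 3 | yes | no | yes |
| 20.1 | 3 and 4 | 4 | yes | yes | yes |

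**Step 2. Size of the difference from the ALT/AST rows.**

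- Start of the Grade 3 or 4 count: 20/5 = 4 times as high.
- Grade 1/2 boundary: 5/2.5 = 2 times as high.

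**Step 3. Patients already above ULN at baseline.**

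- *1.2 to 4.8 x ULN.* Both values are Grade 1, so there is no grade increase and the shift summary says same. On the ALT/AST rows this is Grade 1 to Grade 2. The patient is still counted at >=1.5 x ULN, in the subset with baseline >1 to <1.5 x ULN, and is listed.
- *1.6 to 4.8 x ULN.* The grade is again unchanged. This patient falls in the subset with baseline >=1.5 x ULN, where being counted does not show a rise. The treatment-emergent high analysis (SAP Section 6.14.3) requires values within the limit at all baseline visits, so it excludes this patient. The rise shows only in the listing and in the change-from-baseline summaries.

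**Step 4. What the tie itself affects.** The second criterion pools Grades 3 and 4, so a value above 20 x ULN counts whichever grade is assigned. The tie matters only where Grades 3 and 4 are shown separately, in the shift tables and the summary of grade increases.

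**The case against.** The strongest objection is that the displays still work for most purposes. A reader might infer that the grade tables cannot show ALP rises of clinical size. The SAP does not support that. From a normal baseline every value above ULN meets the any-increase criterion. The shift tables separate >ULN to 5, >5 to 20 and >20 x ULN. ALP >=1.5 x ULN has its own count and listing. This objection stands, and it limits the point to a loss of sensitivity.

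A reader might also infer that the comparison of arms is biased toward no difference. The same cut-offs apply to both arms. A higher cut-off lowers the counts, but nothing in the documents shows a distorted comparison.

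Nor is it given that ALP must share the ALT and AST ladder. Bilirubin has its own steps in the same table, and the CTCAE tables are not reproduced in the documents. That objection stands as far as the exact cut points go: a departure from CTCAE in the lower grades cannot be confirmed here. It does not remove the duplicate top grades, which are visible on the page.

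Finally, the table was read from text extracted from a PDF, so an extraction fault is possible. The ALP rows do form a coherent ladder, with a lost step and a repeated last line, which is unlike stray displaced cells. The printed table should still be checked before anything is changed. If it shows four distinct grades, the point falls.

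**Conclusion.** The point holds as a minor defect in an operative derivation rule. As printed, ALP Grades 3 and 4 cannot be told apart. The Grade 3 or 4 treatment-emergence count misses ALP >5 to 20 x ULN, and movement within >ULN to 5 x ULN does not register as a grade change.

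The factors of 4 and 2 rest on taking the ALT and AST rows as the benchmark. That is likely what was intended but is not established. The conclusion also assumes that the printed SAP matches the text read here and that the program follows the table literally.

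The stakes are limited. ALP is not among the protocol's adverse events of special interest (Protocol Section 10.3.1.1), the laboratory criteria for interrupting or stopping study drug (Protocol Tables JAGS.8.1 and JAGS.8.2), or the axes of the eDISH plot. No efficacy analysis, power or alpha is affected.

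**What to change.** 1. Check the ALP rows in the printed SAP Table 6-3.
2. If they read as above, replace them with the four distinct ALP grades of the CTCAE versions the SAP cites. The ladder at 2.5, 5 and 20 x ULN, already used for ALT and AST in the same table, is the likely intended one. Confirm it against the source before adopting it.
3. Confirm that the laboratory program uses those cut points for the treatment-emergent, shift and follow-up shift tables, and re-run those tables if it does not.

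The cost is one block of a table and one derivation in the laboratory program. No new data are needed.

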6.14.4.2. Myelosuppressive Events

Using clinical laboratory assessments, the myelosuppressive events of anemia, leukopenia, neutropenia, lymphopenia, and thrombocytopenia will be assessed through analysis of decreased

hemoglobin, decreased white cell count, decreased neutrophils absolute count, decreased lymphocytes absolute count, and decreased platelet count, respectively.

Laboratory tests for these measures may be summarized across time points using boxplots which include accompanying summary statistics.

Criteria for AE grading from the CTCAEs will be applied for laboratory tests related to myelosuppressive events (Table 6-4). These CTCAE grading schemes are consistent with both Version 3.0 and Version 4.03 of the CTCAE guidelines. When deriving CTCAE grades for laboratory analytes with absolute criteria for grading, an adjustment to the CTCAE-defined approach will be made. The use of an LLN/ULN from appropriate reference ranges will be replaced with a simpler approach that uses a single value (or a sex-specific pair of values for hemoglobin). This adjustment to the CTCAE grading criteria overcomes the irresolute derivation of the grade that can occur when some demographically-specific LLN/ULN values overlap with the CTCAE-defined value that separates normal (Grade 0) and Grade 1.

Treatment-emergence will be characterized using 2 criteria:

- any increase in post-baseline CTCAE grade from worst baseline grade
- an increase from worst baseline less than Grade 3 to Grade 3 or Grade 4 at worst post-baseline

Table 6-4. Common Terminology Criteria for Adverse Events Related to Myelosuppressive Events

Event	Laboratory Test	Grade	Criteria in SI Units
Anemia	Hemoglobin	0 (normal)	$\geq 7.27 \text{ mmol (Fe)/L}$ for females and $\geq 8.18 \text{ mmol (Fe)/L}$ for males
		1	$<7.27 \text{ mmol (Fe)/L}$ for females and $<8.18 \text{ mmol (Fe)/L}$ for males and $\geq 6.2 \text{ mmol (Fe)/L}$ for both females and males
		2	$<6.2 \text{ mmol (Fe)/L}$ and $\geq 4.9 \text{ mmol (Fe)/L}$
		3	$<4.9 \text{ mmol (Fe)/L}$ and $\geq 4.0 \text{ mmol (Fe)/L}$
		4	$<4.0 \text{ mmol (Fe)/L}$
Leukopenia	White blood cell (WBC) count	0 (normal)	$\geq 4.0 \text{ GI/L}$
		1	$<4.0 \text{ GI/L}$ and $\geq 3.0 \text{ GI/L}$
		2	$<3.0 \text{ GI/L}$ and $\geq 2.0 \text{ GI/L}$
		3	$<2.0 \text{ GI/L}$ and $\geq 1.0 \text{ GI/L}$
		4	$<1.0 \text{ GI/L}$
Neutropenia	Absolute neutrophil count (ANC)	0 (normal)	$\geq 2 \text{ GI/L}$
		1	$<2 \text{ GI/L}$ and $\geq 1.5 \text{ GI/L}$
		2	$<1.5 \text{ GI/L}$ and $\geq 1.0 \text{ GI/L}$
		3	$<1.0 \text{ GI/L}$ and $\geq 0.5 \text{ GI/L}$
		4	$<0.5 \text{ GI/L}$
Lymphopenia	Lymphocyte count	0 (normal)	$\geq 1.1 \text{ GI/L}$
		1	$<1.1 \text{ GI/L}$ and $\geq 0.8 \text{ GI/L}$
		2	$<0.8 \text{ GI/L}$ and $\geq 0.5 \text{ GI/L}$
		3	$<0.5 \text{ GI/L}$ and $\geq 0.2 \text{ GI/L}$
		4	$<0.2 \text{ GI/L}$
Thrombocytopenia	Platelet count	0 (normal)	$\geq 150 \text{ GI/L}$

1	<150 GI/L and ≥ 75 GI/L
2	<75 GI/L and ≥ 50 GI/L
3	<50 GI/L and ≥ 25 GI/L
4	<25 GI/L

Abbreviations: ANC = absolute neutrophil count; dL = deciliters; Fe = iron; g = grams; GI/L = Giga/Liter; mmol = millimoles; SI = Système International; WBC = white blood cell.

A laboratory-based treatment emergent outcome related to increased platelet count will be summarized in similar fashion. Treatment-emergent thrombocytosis as a laboratory-based abnormality will be defined as an increase in platelet count from a maximum baseline value $\leq 600,000/\mu\text{L}$ to any postbaseline value $> 600,000/\mu\text{L}$. A frequency table showing the number and percent of patients meeting criteria for thrombocytosis by treatment group will be provided. Scheduled and unscheduled measurements will be included.

Shift tables will show the number and percent of patients with measurement in each category based on baseline to maximum grade during the treatment period, with baseline depicted by the most extreme grade during the baseline period. With each shift table, a shift table summary will display the number and percent of patients with maximum postbaseline results overall and by treatment group within the following categories:

- Decreased; postbaseline category $<$ baseline category,
- Increased; postbaseline category $>$ baseline category,
- Same; postbaseline category = baseline category.

Scheduled and unscheduled measurements will be included. Treatment differences for the shift table summary categorizations may be assessed with the Likelihood Ratio Chi-Square test, using the exact version of this test whenever at least 1 cell has an expected cell count < 5 . Furthermore, a summary of grade increases by each maximum grade will be provided.

The number and percent of patients with measurement in each category based on baseline to CTCAE grade at each scheduled visit during the treatment period, with baseline depicted by the last grade during the baseline period, will be further summarized in terms of shift tables by time point and last visit and by treatment group. Only scheduled measurements will be included in these analyses. Following the shift table for the last visit, a shift table summary of the last visit will be included. Furthermore, a summary of grade increases by each grade at last visit will be provided.

The number and percent of patients with treatment-emergent lab abnormalities related to myelosuppression based on CTCAE grades will be summarized in terms of shift tables descriptively comparing baseline to maximum and last post-treatment follow-up grade and follow-up baseline to maximum and last post-treatment follow-up grade by treatment group. A shift table summary for each analysis will also be included. Furthermore, a summary of grade increases by each maximum and last grade will be provided.

First shift table summary:

- Decreased; maximum post-treatment follow-up category $<$ baseline category

- Increased; maximum post-treatment follow-up category > baseline category
- Same; maximum post-treatment follow-up category = baseline category

Second shift table summary:

- Decreased; maximum post-treatment follow-up category < follow-up baseline category
- Increased; maximum post-treatment follow-up category > follow-up baseline category
- Same; maximum post-treatment follow-up category = follow-up baseline category

Third shift table summary:

- Decreased; last post-treatment follow-up category < baseline category
- Increased; last post-treatment follow-up category > baseline category
- Same; last post-treatment follow-up category = baseline category

Fourth shift table summary:

- Decreased; last post-treatment follow-up category < follow-up baseline category
- Increased; last post-treatment follow-up category > follow-up baseline category
- Same; last post-treatment follow-up category = follow-up baseline category

6.14.4.3. Lipids Effects

Lipids effects will be assessed through analysis of elevated total cholesterol, elevated LDL cholesterol, decreased HDL cholesterol, and elevated triglycerides.

National Cholesterol Education Program (NCEP) Adult Treatment Panel III will be applied for laboratory tests related to lipids effects (Table 6-5). The grade-like categories shown in this table are ordered from lowest to highest for the purposes of these analyses.

Table 6-5. National Cholesterol Education Adult Treatment Panel III Criteria

Lab Test	Category	Criteria in SI Units
Total Cholesterol	Desirable	<5.17 mmol/L
	Borderline high	≥5.17 mmol/L and <6.21 mmol/L
	High	≥6.21 mmol/L
LDL-C	Optimal	<2.59 mmol/L
	Near optimal	≥2.59 mmol/L and <3.36 mmol/L
	Borderline high	≥3.36 mmol/L and <4.14 mmol/L
	High	≥4.14 mmol/L and <4.91 mmol/L
	Very high	≥4.91 mmol/L
HDL-C	High	≥1.55 mmol/L
	Normal	≥1.03 mmol/L and <1.55 mmol/L
	Low	<1.03 mmol/L
Triglycerides	Normal	<1.69 mmol/L
	Borderline high	≥1.69 mmol/L and <2.26 mmol/L
	High	≥2.26 mmol/L and <5.65 mmol/L
	Very high	≥5.65 mmol/L

Abbreviations: HDL-C = high-density lipoprotein cholesterol; LDL-C = low-density lipoprotein cholesterol.

Treatment-emergent laboratory abnormalities related to elevated total cholesterol, elevated LDL cholesterol, decreased HDL cholesterol, and elevated triglycerides occurring at any time during the treatment period will be tabulated using the NCEP categories shown in [Table 6-5](#).

Treatment-emergent elevated total cholesterol will be characterized as movement from categories 'Desirable' or 'Borderline High' to category 'High' considering patients who are at risk for the abnormality, that is, not 'High' based on the maximum baseline total cholesterol category. Treatment-emergent elevated LDL cholesterol will be characterized as movement from categories 'Optimal,' 'Near optimal,' or 'Borderline high' to categories 'High' or 'Very high' considering patients who are at risk for the abnormality, that is, neither 'High' nor 'Very high' based on the maximum baseline LDL cholesterol category. Treatment-emergent decreased HDL cholesterol will be characterized as movement from categories 'High' or 'Normal' to category 'Low' considering patients who are at risk for the abnormality, that is, not 'Low' based on the minimum baseline HDL cholesterol category. Treatment-emergent elevated triglycerides will be characterized as movement from categories 'Normal' or 'Borderline high' to categories 'High' or 'Very high' considering patients who are at risk for the abnormality, that is, neither 'High' nor 'Very high' based on the maximum baseline triglycerides category. Scheduled and unscheduled measurements will be included.

Shift tables will show the number and percent of patients with measurement in each category based on baseline to maximum or minimum category during the treatment period, with baseline depicted by the most extreme category during the baseline period. With each shift table, a shift table summary will display the number and percentage of patients with maximum or minimum postbaseline results overall and by treatment group within the following categories:

- Decreased; postbaseline category < baseline category,
- Increased; postbaseline category > baseline category,
- Same; postbaseline category = baseline category.

Treatment differences for the shift table summary categorizations may be assessed with the Likelihood Ratio Chi-Square test, using the exact version of this test whenever at least 1 cell has an expected cell count <5. Furthermore, a summary of category increases by each maximum category will be provided.

In addition, the number and percent of patients with measurement in each category based on baseline to NCEP category at each scheduled time point, with baseline depicted by the last category during the baseline period, will be further summarized in terms of shift tables by time point and last visit and by treatment group. Only scheduled measurements will be included in these analyses. Following the shift table for the last visit, a shift table summary of the last visit will be included. Furthermore, a summary of category increases by each category at last visit will be provided.

